A Dose Escalation and Safety Committee (DESC) consisting of sponsor representatives and investigators will convene once a dose level cohort completes the DLT observation period and data are available for review. Additional details regarding responsibilities, membership requirements and safety review time points are included in the DESC Charter. The DESC will also review the aggregate safety data from the phase 1 dose escalation and phase 2 expansion cohorts.

While safety data from the DLT observation period in the escalation cohorts are the minimum safety data needed for the DESC meeting, all available safety findings will be considered by the DESC. The DESC will assess whether a longer DLT observation period is warranted based on emerging data. Additionally, only when determining the RP2D, the DESC may choose a more conservative dosing decision than the maximum tolerated dose (MTD) selected by BOIN design, based on evaluation of the safety data and other available data.

The decision on the dose level for the next cohort will be based on the BOIN design. In addition, MTD will be determined by BOIN from at least 6 participants. The dose for phase 2 expansion will not be higher than the MTD.

Participant Replacement during Dose Escalation Cohort

Participants may be replaced in the dose escalation cohort if:

- Participant is discovered to have enrolled without fully satisfying eligibility criteria
- Participant received less than the planned dose in Cycle 1 for reasons other than DLT
- Participant has no DLT and withdraws from the study before the end of DLT evaluation period

The decision regarding replacement of individual participants will be made by the sponsor with discussions with the treating investigator. Participants who experience DLTs in the dose escalation cohort will not be replaced.

Dose evaluation and dose escalation stopping rules based on the BOIN design with target DLT rate of 0.30 and optimal interval of (0.236, 0.359) are as follows:

Action	Number of Participants Treated at Current Dose Level					
	3	4	5	6	7	8
Escalate dose if number of participants with DLT \leq	0	0	1	1	1	1
Stay at current dose level if number of participants with DLT =	1	1	-	2	2	2
De-escalate if number of participants with DLT =	2	2	2 or 3	3	3 or 4	3 or 4
Stop if number of participants with DLT \geq	3	3	4	4	5	5

DLT: dose limiting toxicity

Dose escalation within individual participants will not be allowed.

Maximum Tolerated Dose

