4.1.4 Dose Limiting Toxicity Criteria

A DLT is defined as any of the following events that occur within 28 days starting with the first dose on Cycle 1 Day 1 (C1D1) and that is considered to be related to IP. Confirmation of DLTs will be made by the DESC. The severity of AEs will be assessed according to the National Cancer Institute's Common Terminology Criteria for Adverse Events (NCI-CTCAE), version 5.0.

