4.1.5.2 Phase 1 Dose Escalation Cohort for Monotherapy and Combination Therapy Arms

The monotherapy and combination therapy dose escalation portion will evaluate escalating dose levels of ASP7517 in approximately 9 to 12 DLT-evaluable participants.

Dose escalation will be guided according to the BOIN design [Liu & Yuan, 2015] to determine the next dose level based on DLT occurrence. After the planned number of evaluable participants has completed the DLT observation period for a given dose level, safety for that dose level will be assessed. Each dose level in the dose escalation will enroll

3 to 4 evaluable participants for the initial assessment of each dose level. Refer to the *Participant Replacement during Dose Escalation Cohort* section for definition of evaluable participants. If the decision is made to remain at the current dose level, an additional 3 or 4 evaluable participants may be enrolled at the current dose level. Three to 12 participants will be enrolled in the dose escalation cohort. A minimum of 6 participants must be enrolled at the dose level used to determine the maximum tolerated dose (MTD) and the recommended phase 2 dose (RP2D) of ASP7517.

Study enrollment and study treatment will be temporarily interrupted during dose escalation of monotherapy or combination therapy arms pending review of the following:

- Any death that is not related to disease progression occurring within 30 days of receiving IP
- Occurrence of 2 grade ≥ 4 DLTs in 2 study participants
- Any grade 4 hypersensitivity reaction/anaphylaxis

Participant Replacement during Dose Escalation Cohort

Participants may be replaced in the dose escalation cohort if:

- Participant is discovered to have enrolled without fully satisfying eligibility criteria
- Participant received less than the planned dose in Cycle 1 for reasons other than DLT
- Participant has no DLT and withdraws from the study before the end of DLT evaluation period

The decision regarding replacement of individual participants will be made by the sponsor with discussions with the treating investigator.

Participants who experience DLTs in the dose escalation cohort will not be replaced.

Refer to [\[Section 10.1.5.1 Dose Escalation and Safety Committee\]](#) for details about the DESC.

Maximum Tolerated Dose

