8.2 Discontinuation of Individual Participant(s) from Study

All participants who discontinue study treatment will remain in the study and must continue to be followed for protocol-specific follow-up procedures as outlined in the schedules of assessments [Table 3 to Table 6]. The only exception to this is when the participant specifically withdraws consent for any further contact with him/her or persons previously authorized by the participant to provide this information.

All participants who discontinue study treatment are to be followed for up to 12 months after their end of treatment, death or the final analysis, whichever occurs first per the schedules of assessments [Table 3 to Table 4].

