9.3 Populations for Analyses

The following populations are defined:

Population	Description
Enrolled	All participants who sign the informed consent form are allocated to treatment
Full Analysis Set (FAS)	All participants who are enrolled and receive at least one dose of study treatment.
Response Analysis Set (RAS)	The RAS will consist of all participants who are enrolled and receive at least 1 dose of IP and have at least 1 post baseline primary efficacy measurement.
Safety Analysis Set (SAF)	All participants who take at least one dose of IP.
Pharmacokinetic analysis set (PKAS)	The PKAS consists of the administered population for which pharmacokinetics data are available for at least 1 time point. Additional participants may be excluded from the PKAS at the discretion of the pharmacokineticist.
Pharmacodynamic analysis set (PDAS)	The PDAS will include the participants from the administered population for whom sufficient pharmacodynamic measurements were collected. The PDAS will be used for all analyses of pharmacodynamic data.
DLT Evaluation Analysis Set (DEAS)	
The DEAS is defined as all participants in SAF by excluding participants who meet any of the following criteria:
 
• Participant is discovered to have enrolled without fully satisfying eligibility criteria.• Participant received less than the planned dose in Cycle 1 for reasons other than DLT.• Participant has no DLT and withdraws from the study before the end of DLT evaluation period 
The DEAS will be used for the analysis of DLT data.

DLT: dose limiting toxicity

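### The DLT evaluation set and the replacement list have no minimum-observation criterion, which conflicts with the completion condition in Protocol 4.1.5.2

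*Protocol*

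**What the plan says.** Protocol 9.3 builds the DLT evaluation analysis set (DEAS) from the safety set by three exclusions: ineligible participants, those given less than the planned Cycle 1 dose for non-DLT reasons, and the case "Participant has no DLT and withdraws from the study before the end of DLT evaluation period". SAP 4 repeats the three. The replacement list in the synopsis and in Protocol 4.1.5.2 has the same three items, and 4.1.5.2 points to that list with the words "section for definition of evaluable participants".

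On leaving treatment, Protocol 8.1 lists progression, start of other anticancer therapy, loss to follow-up and death as reasons for stopping study treatment. Protocol 8.2 then says: "All participants who discontinue study treatment will remain in the study and must continue to be followed", and "The only exception to this is when the participant specifically withdraws consent for any further contact".

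A DLT is "any of the following events that occur within 28 days starting with the first dose on Cycle 1 Day 1 (C1D1") and judged related to investigational product (Protocol 4.1.4). On dose decisions the synopsis says: "The decision on the dose level for the next cohort will be based on the BOIN design". Section 4.1.5.2 adds that a dose level is assessed after the planned number of evaluable participants has finished the DLT observation period.

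**The concern.** A DLT-free result means something only if the participant was watched for the whole 28-day window. The two lists enforce this for participants who withdraw from the study and for no one else. A participant who dies of progression on Day 10, or starts chemotherapy on Day 11, has not withdrawn in the sense of 8.2. The under-dosing exclusion does not catch them either: ASP7517 is given once per cycle, on Day 1, and pembrolizumab every 6 weeks from Cycle 1 Day 1, so the whole Cycle 1 dose is already in. A progression death is not related to treatment and so is not a DLT.

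Such a participant stays in the DLT denominator as DLT-free. Shortened follow-up can miss a DLT but cannot add one, so the error has one direction: a lower observed DLT rate. That rate feeds the BOIN (Bayesian optimal interval) table, the isotonic estimate behind the MTD, and the requirement for at least 6 evaluable participants.

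**Working it through.** **1. The texts side by side.**
- DEAS and replacement lists: completion of 28 days is not required, and the only exit for short observation is study withdrawal.
- Protocol 8.1 and 8.2: progression death and change of therapy are treatment discontinuation, not study withdrawal.
- Protocol 4.1.5.2: assessment waits until evaluable participants have completed the window.

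A participant who died on Day 10 is evaluable by the list, cannot complete the window, and is not on the list of those who may be replaced. The cohort then stalls or is assessed with that participant included. The text does not say which. The DEAS, which governs the DLT analysis, has no completion condition at all.

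**2. The plan's own figures.** The synopsis gives a "target DLT rate of 0.30 and optimal interval of (0.236, 0.359"). Assuming the usual BOIN defaults (0.6 and 1.4 times the target, i.e. 0.18 and 0.42; not stated in the documents):
- λe = ln(0.82/0.70) / ln[(0.30×0.82)/(0.18×0.70)] = 0.2365
- λd = ln(0.70/0.58) / ln[(0.42×0.70)/(0.30×0.58)] = 0.3585

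Both match. With a stop rule of P(rate > 0.30 | data) > 0.95 under a Beta(1,1) prior (also assumed), every table cell for n = 3 to 8 reproduces. The row "Escalate dose if number of participants with DLT" ≤ gives 0 at n = 3 or 4 and 1 at n = 5 to 8.

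**3. What one truncated participant changes in the table.** Removing a DLT-free participant turns 1/5 (escalate) into 1/4 (stay), and 2/6 (stay) into 2/5 (de-escalate). It turns 0/3 (escalate) into 0/2, for which the table has no column.

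**4. Chance of 0/3.** Assume uniform onset over 28 days, so a participant followed for a fraction f of the window shows a DLT with probability f×p.

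*Cohort containing one participant followed to Day 10:*
- p = 0.40, full observation: 0.6³ = 0.216. One truncated: 0.6² × (1 − 0.40×10/28) = 0.36 × 0.857 = 0.309.
- p = 0.50: 0.5³ = 0.125. One truncated: 0.25 × (1 − 0.50×10/28) = 0.205.

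*Averaged over all cohorts of 3, p = 0.40, with a proportion q truncated at Day 10 (5% to 15%, assumed):* the chance of no observed DLT per participant is 0.6(1 − q) + 0.857q = 0.6 + 0.257q.
- q = 0.05: 0.6129³ = 0.230, a rise of 1.4 points.
- q = 0.15: 0.6386³ = 0.260, a rise of 4.4 points.
- Chance that a cohort of 3 contains at least one: 1 − 0.95³ = 14%, to 1 − 0.85³ = 39%.

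*Other rates and fractions, one of three truncated, (1 − p)²(1 − fp):*

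| True rate | Full | f = 0.75 | f = 0.50 | f = 0.25 |
|---|---|---|---|---|
| 0.30 | 0.3430 | 0.3797 | 0.4165 | 0.4532 |
| 0.42 | 0.1951 | 0.2304 | 0.2658 | 0.3011 |
| 0.50 | 0.1250 | 0.1562 | 0.1875 | 0.2188 |

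With six participants, one of them half-observed, the chance of at most 1 DLT goes from 0.4202 to 0.4742 at p = 0.30 and from 0.2035 to 0.2534 at p = 0.42.

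**The case against.** The strongest reply is that 4.1.5.2 sets two conditions, evaluable and window completed, and the list defines only the first. The synopsis likewise convenes the Dose Escalation and Safety Committee once a cohort completes the window. A reader might infer from the lists alone that the plan lets the trial escalate on incomplete observation. The documents do not support that: read strictly, a Day 10 death cannot fill a slot. What remains is a conflict, because the lists neither mirror the completion condition nor allow that participant to be replaced.

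Second, participants who switch therapy must still be followed under 8.2, and treatment-emergent events run to 30 days after the last dose, so their observation is not necessarily lost. This stands in part. Protocol 4.1.1 lets the safety visits be done before new anticancer therapy starts, and nothing says whether later observation counts toward the DLT window. Death is the clear case.

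Third, toxicity is largely covered. Related toxicity that stops treatment in Cycle 1 and related Grade 5 events are already DLTs, so only exits judged unrelated fall in the gap.

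Fourth, the size is uncertain. The documents give no rate of early exit. The first scheduled scan is at Day 56 ± 7, so a change of therapy before Day 28 needs clinical progression or unscheduled imaging. Protocol 4.3.1 reports no DLTs in the earlier ASP7517 study at the doses assessed. Early-onset toxicity would shrink the effect, while immune-related events on pembrolizumab can come later. All of this stands.

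**Conclusion.** The gap holds as an inconsistency. The DEAS and the evaluability list count a DLT-free participant with truncated follow-up, while 4.1.5.2 requires completion. In the DLT analysis such a participant is DLT-free by rule; in escalation the outcome is undefined. Any bias is downward.

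The general effect on 0/3 is 1.4 to 4.4 points at a true rate of 40%, given 5% to 15% truncated at Day 10 and uniform onset. The rise to 30.9% applies only to a cohort that contains one such participant and should not be read as the overall effect. Nor is every BOIN decision biased: cohorts without such a participant are untouched, there is one upward step from the starting dose, and the RP2D may be set below the MTD.

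SAP 5.1.1 reports early closure of the study, so the remaining effect may be mainly on how DLT rates and any MTD are reported. SAP version 2.0 still carries the same DEAS.

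**What to change.** In Protocol 9.3, 4.1.5.2 and the synopsis, and in SAP 4, replace the third criterion with: *Participant has no DLT and does not complete the 28-day DLT observation period for any reason.* Such participants become non-evaluable and replaceable, and every participant with a DLT stays counted. State also whether observation after the start of a new anticancer therapy counts as complete.

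The cost is one sentence in each place, plus an occasional replaced participant under the process that already exists.

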9.4 Statistical Analyses

A statistical analysis plan (SAP) will be written to provide details of the analysis, along with specifications for tables, listings and figures to be produced. Changes from the planned analyses in the final SAP that impact the statistical analyses will be justified in the clinical study report (CSR).

9.4.1 General Considerations

In general, data will be summarized with descriptive statistics for continuous endpoints, and frequency and percentage for categorical endpoints, unless otherwise specified. Percentages by categories will be based on the number of participants with no missing data (i.e., will add up to 100%).

Baseline will be defined as the last non-missing observation prior to first administration of IP, unless otherwise specified.

Demographics and baseline characteristics will be summarized by monotherapy and combination therapy arms, and dose level, and overall for all treated participants.

The number and percentage of participants who completed and discontinued treatment and reasons for treatment discontinuation will be presented for all enrolled participants and for participants in the safety analysis set (SAF) by monotherapy and combination therapy arms, and dose level, and overall. Similar tables for screening disposition, observation period disposition and follow-up disposition will also be presented for all treated participants by monotherapy and combination therapy arms, and dose level, and overall. All disposition details and dates of first and last evaluations for each participant will be listed.

Previous and concomitant treatment and medical history will be listed. Investigational product exposure will be summarized by descriptive statistics and will be listed.

9.4.2 Analysis of Efficacy

Binary efficacy endpoint analysis will be conducted on RAS while time to event endpoints will be conducted on FAS. The interpretation of results of the primary efficacy endpoint will be based on RAS. Efficacy analyses will be summarized by monotherapy and combination therapy and dose level. Tumor related analyses are summarized based on RECIST v1.1 and iRECIST.

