4.1.2 ASP7517 Monotherapy Arm in Dose Escalation Phase 1 Cohort

For ASP7517 Monotherapy Arm in Dose Escalation portion participants will receive 1 dose of ASP7517 on Day 1 of each 28-day cycle for up to 6 doses. Following the first 2 cycles, participants who have not met any individual treatment discontinuation criteria and are receiving clinical benefit (defined as radiological response or stable disease [SD], or reduction of disease-related symptoms) may continue further treatment with ASP7517, as decided by the investigator.

Participants who achieve confirmed complete response (CR) within the first 4 cycles will not receive further treatment with ASP7517, and participants who achieve partial response (PR) or SD after 4 doses may receive an additional 2 doses. An EOT visit will be conducted for all participants within 7 days of EOT determination or prior to the initiation of new anticancer therapy, whichever occurs first.

The starting dose level is 1×10^7 cells/dose and the decision to escalate to the next dose level (1×10^8 cells/dose) will be made based on the assessment of safety variables, including the occurrence of dose limiting toxicities (DLTs). Dose level may be de-escalated to a lower dose level (1×10^6 cells/dose) based on the occurrence of DLTs.

After the EOT visit, participants will complete 30-day, 60-day and 90-day safety follow-up visits from the last dose of ASP7517 or prior to the initiation of new anticancer therapy.

All participants will enter an observation period except those with confirmed disease progression by immune response evaluation criteria in solid tumors (iRECIST) (iCPD), unconfirmed disease progression based on iRECIST (iUPD) (per independent central review or local review) and who are not clinically stable or clinical progression is confirmed by the investigator. Participants in the Monotherapy Arm Observation Period will be followed for up to 48 weeks starting at EOT until iCPD per independent central review, initiation of a new

anticancer therapy or meeting 1 of the Observation Period discontinuation criteria, whichever occurs first. Safety Follow-up period is included in Observation Period.

All participants will be followed for survival, subsequent anticancer treatments and treatment outcomes following the conclusion of the Observation Period.

Refer to [Section 4.1.5] for additional dose escalation cohort management details.

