5.1.2.5 Progression-free Survival per iRECIST (iPFS)

iPFS is defined as the time from the start of the study treatment until death from any cause or radiographic disease progression assessed per iRECIST by investigator assessment, whichever occurs first.

If iUPD occurs but iSD, iPR, or iCR is observed any time subsequent to iUPD, iUPD status will be disregarded for determination of iPFS.

Table 2 iPFS Definition

iPFS		
Situation	Date of Event or Censor	Outcome
No evaluable post-baseline imaging assessments, no death	Date of first dose (Day 1)	Censor
Participant did not receive new anti-cancer therapy:		
iCPD	First date where iUPD criteria are met	Event
No iCPD, but death recorded on eCRF	Date of death	Event
No iCPD nor death and not in one of the following cases :a)if the participant stops protocol treatment because they were not judged to be clinically stable, b) no further response assessments are done (because of participant refusal, protocol non-compliance, or participant death); c) the	Date of last radiological assessment	Censor

iPFS		
Situation	Date of Event or Censor	Outcome
next timepoint responses are all iUPD, and iCPD never occurs;		
No iCPD nor death and is in one of the following cases : a)if the participant stops protocol treatment because they were not judged to be clinically stable, b) no further response assessments are done (because of participant refusal, protocol non-compliance, or participant death); c) the next timepoint responses are all iUPD, and iCPD never occurs;	First date where iUPD criteria are met	Event
Participant received new anti-cancer (ACT) therapy:		
No progression before new ACT	Date of last radiological assessment before start of new anti-cancer therapy	Censor
iCPD before new ACT	First date where iUPD criteria are met	Event
iUPD before new ACT and not in one of the following cases : a)if the participant stops protocol treatment because they were not judged to be clinically stable, b) no further response assessments are done (because of participant refusal, protocol non-compliance, or participant death); c) the next timepoint responses are all iUPD, and iCPD never occurs;	Date of last radiological assessment before start of new anti-cancer therapy	Censor

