5.1.2.6 Progression-free Survival per RECIST v1.1 (PFS)

PFS is defined as the time from the start of the study treatment until death from any cause or radiographic disease progression assessed per RECIST v1.1 by investigator assessment, whichever occurs first.

Table 3 PFS Definition

PFS		
Situation	Date of Event or Censor	Outcome
No evaluable post-baseline imaging assessments, no death	Date of first dose (Day 1)	Censor
Participant did not receive new anti-cancer therapy:		
Radiographical progression documented per RECIST v1.1	Date of radiological disease progression	Event

PFS		
Situation	Date of Event or Censor	Outcome
No radiographical progression, but death recorded on eCRF	Date of death	Event
Neither radiographical progression nor death	Date of last disease assessment	Censor
Participant received new anti-cancer (ACT) therapy:		
Radiographical progression documented per RECIST v1.1 after new ACT	Date of last radiological assessment before start of new anti-cancer therapy	Censor
Radiographical progression documented per RECIST v1.1 before new ACT	Date of radiological disease progression	Event
No radiographical progression before new ACT but death recorded	Date of last radiological assessment before start of new anti-cancer therapy	Censor
No radiographical disease progression nor death	Date of last radiological assessment before start of new anti-cancer therapy	Censor
Missed >=2 scheduled radiological assessments		
If radiographical progression or death occurs after missing 2 scheduled radiological assessments	Date of last radiological assessment before missing 2 scans	Censor

PFS = Date of Event or Censor – Date of First Dose +1

Missing 2 scheduled imaging assessments:

Missing 2 scheduled imaging assessments is defined as the gap between two imaging assessments being more than 140 days (2.5 times the scheduled imaging assessment interval (2.5 x 56 days)). Imaging assessments after first iUPD will be excluded in PFS derivation.

Note: Participant cannot be censored at “NE”. If NE is the only previous assessment, then PFS will be censored at Day 1.

To apply the cut-off date to PFS is to exclude those tumor assessments after cut-off date and anti-cancer therapy date after cut-off date in the analysis.

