6.4 Analysis of Efficacy

Efficacy analysis will be conducted on the FAS and RAS (RAS for response-related analyses, FAS for overall survival and other time-to-event analyses). Tumor related analyses are summarized based on RECIST 1.1 and iRECIST. Efficacy analyses will be summarized by dose level, phase, and tumor type. Swimmer plots will be produced displaying participants' overall disease response experience, and waterfall plots to display maximum tumor shrinkage rate.

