6.4.1 Analysis of Primary Efficacy Endpoint

6.4.1.1 Objective Response Rate per iRECIST (iORR)

iORR with confirmed response by investigator assessment will be calculated for each group and its 95% confidence interval will be constructed by Clopper-Pearson method. To assess sensitivity, iORR will also be estimated and its 95% confidence interval will be constructed by Clopper-Pearson method for the endpoints:

- iORR with confirmed response by investigator assessment
- iORR with unconfirmed response by investigator assessment

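### Response and disease control rates are planned only on the Response Analysis Set, which drops treated participants with no post-baseline assessment; no all-treated (FAS) estimate is prespecified

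*Protocol*

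**What the plan says.** Protocol 9.4.2 assigns binary efficacy endpoints to the RAS and time-to-event endpoints to the FAS, and adds: "The interpretation of results of the primary efficacy endpoint will be based on RAS". Protocol 9.3 and SAP 4 define both sets. The FAS is everyone enrolled and dosed. The RAS is the same group with one more condition, that they "have at least 1 post baseline primary efficacy measurement".

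SAP 4 names both sets for efficacy, but SAP 6.4 divides the work between them: "RAS for response-related analyses, FAS for overall survival and other time-to-event analyses". The general mention in SAP 4 therefore does not supply a response rate on the FAS.

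The sensitivity analyses do not change the denominator. Protocol 9.4.2.2 varies the reader and whether response is confirmed. SAP 6.4.1.1 first sets the main analysis as confirmed iORR by the investigator, then says: "To assess sensitivity, iORR will also be estimated and its 95% confidence interval will be constructed by Clopper-Pearson method for the endpoints". Two bullets follow, confirmed and unconfirmed response, both by the investigator. The first is the main analysis again. SAP 6.4.2.1 to 6.4.2.3 handle ORR, iDCR and DCR with the same confirmed/unconfirmed pair and no second analysis set.

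**The concern.** Leaving the RAS depends on what happens to the participant after dosing, and it can move the result in one direction only. Protocol 7.1 schedules imaging every 8 weeks (plus or minus 1 week) from the first dose, and confirmation of a response takes a further scan at least 4 weeks later. Someone who dies, withdraws or deteriorates before the first scan can have no response of any kind, yet disappears from the denominator.

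The protocol also contains a route to having no scan. The observation period, which carries post-treatment imaging, excludes participants with unconfirmed progression "who are not clinically stable or clinical progression is confirmed by the investigator".

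Early closure makes the reported rate more important. SAP 5.1.1 says that only investigator-assessed endpoints will be presented, and SAP 6.4 breaks them down by dose level, phase and tumor type. In small groups, one or two exclusions move the rate visibly.

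**Working it through.** **Plan's own figures first.** Protocol 9.2 claims about 0.80 power at one-sided type I error 0.05. The boundaries in Protocol 4.1.6 and the rates in Protocol 9.1 give the exact two-stage probability P(X1 > r1 and X1 + X2 ≥ r), where r1 is the stage 1 stopping count and r the final success count:

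| Cohort | Stage 1 n, stop if ≤ | Final n, success if ≥ | Type I error | Power |
|---|---|---|---|---|
| Monotherapy | 18, 2 | 43, 8 | 0.048 | 0.800 |
| CPI-naïve melanoma | 20, 4 | 69, 24 | 0.042 | 0.820 |
| Ovarian | 19, 3 | 55, 13 | 0.048 | 0.801 |
| CRC | 21, 4 | 60, 16 | 0.050 | 0.805 |
| CPI-refractory melanoma | 20, 2 | 48, 11 | 0.039 | 0.809 |

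The design reproduces. The point concerns the reported estimate, not the sample size.

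**Direction.** Let N be the number treated, m the number with no post-baseline assessment, x the number of responders (or with disease control), and d = m/N. None of the m can be among the x. Then

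- all-treated (FAS) rate = x/N
- RAS rate = x/(N − m) = (x/N) × 1/(1 − d)

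The RAS rate is never below the FAS rate. The two are equal when m = 0 or x = 0. With x = 0 the estimate stays at 0% and only the upper 95% limit moves, for example from 18.5% (0/18) to 20.6% (0/16).

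**Size.** The documents give no d, so m and x below are assumptions. Intervals are two-sided 95% Clopper-Pearson, as the plan specifies. The sizes 43 and 18 are the planned monotherapy maximum and stage 1.

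| Case | All treated | RAS | Factor |
|---|---|---|---|
| Response, m = 2 | 8/43 = 18.6% (8.4 to 33.4) | 8/41 = 19.5% (8.8 to 34.9) | 43/41 = 1.05 |
| Response, m = 4 | same | 8/39 = 20.5% (9.3 to 36.5) | 43/39 = 1.10 |
| Response, m = 6 | same | 8/37 = 21.6% (9.8 to 38.2) | 43/37 = 1.16 |
| Response, stage 1, m = 2 | 3/18 = 16.7% (3.6 to 41.4) | 3/16 = 18.8% (4.0 to 45.6) | 18/16 = 1.13 |
| Disease control, m = 4 | 20/43 = 46.5% (31.2 to 62.3) | 20/39 = 51.3% (34.8 to 67.6) | 1.10 |
| Disease control, m = 6 | same | 20/37 = 54.1% (36.9 to 70.5) | 1.16 |

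The factor is the same for response and disease control, so the absolute shift grows with the rate. With 4 excluded it is 20.5 − 18.6 = 1.9 points for response and 51.3 − 46.5 = 4.8 points for disease control.

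**Comparison with the time-to-event tables.** iPFS and PFS use the FAS. Their tables foresee a participant with "No evaluable post-baseline imaging assessments, no death" and censor that participant at Day 1. They count as events "No iCPD, but death recorded on eCRF" (iPFS) and "No radiographical progression, but death recorded on eCRF" (PFS). An early death with no scan can therefore be a failure for iPFS or PFS and absent from iORR. The contrast holds only for deaths that those tables count as events.

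**The case against.** The choice is disclosed. Both documents define the RAS and assign it consistently, and an evaluable-set response rate is not a contradiction in an early-phase design. That stands, and it is why this is a missing analysis rather than an error.

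The shift is small and hypothetical. In the response example with N = 43 it is 0.9 to 3.0 points, inside an interval 25.0 points wide (33.4 − 8.4), and no document shows that any cohort reached the planned size. That also stands. But the shift has one direction, and enrolling more participants does not remove it.

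A reader can rebuild the rate. SAP 4 and SAP 6.2.1 tabulate analysis-set counts, and SAP 4 does so by dose level. This works in part. Efficacy is also split by phase and tumor type, for which set counts are not clearly promised, and no all-treated interval is specified.

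Three stronger readings are tempting, and the documents do not support them:

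- *That the excluded are mainly early deaths, clinical progressions and withdrawals.* This is plausible but inferred. Protocol 8.2 keeps participants in follow-up after treatment stops, and Protocol 7.1 continues imaging through interruptions.
- *That iPFS and PFS treat all such participants as failures.* They do not. Living participants with no scan are censored at Day 1. In the iPFS table, so is a death after two missed scans with no earlier post-baseline imaging.
- *That the go/no-go rule has inflated type I error.* The boundary tables count participants treated, and on that count the error is 0.039 to 0.050. It would exceed 0.05 (monotherapy 0.061 at d = 5%) only if every non-evaluable participant were replaced, boundaries counted evaluable participants, and H0 were a rate among treated. The plan does not state that combination. Replacement is discretionary, and SAP 6.8 performs no interim analysis.

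**Conclusion.** The point holds as a gap in the analysis plan. All four binary efficacy rates rest on a set that removes treated participants who cannot count as successes. No all-treated version is prespecified, and one of the two sensitivity analyses for the primary endpoint repeats the main one. The reported rate equals or exceeds the all-treated rate by the factor 1/(1 − d): about 1.05 to 1.16 if 2 to 6 of 43 are excluded.

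The direction rests on reading a post-baseline efficacy measurement as a tumor assessment, which is the natural reading. The size rests on an assumed d, and on assumed responder and disease-control counts. The sample size, stopping boundaries and planned error rates are not in question.

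**What to change.** In SAP 6.4.1.1, replace the duplicated first sensitivity bullet with:

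> Confirmed iORR by investigator assessment on the FAS, with participants who have no post-baseline tumor assessment counted as non-responders.

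Add the same FAS analysis for ORR, iDCR and DCR in SAP 6.4.2.1 to 6.4.2.3, where no assessment means no response and no disease control. State the rule explicitly, because Protocol 9.4.1 and SAP 6.1 base percentages on participants with non-missing data, which would otherwise drop the same people again.

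Preferably, make the FAS the main set for these four rates in Protocol 9.4.2 and SAP 6.4, and keep the RAS as supportive.

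No new data are needed. The cost is a few more table rows and possibly a slightly lower reported rate. For iORR the new analysis takes the place of one that adds nothing.
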